#### IV. Research Methods

[figure not shown]
##### A. Outcome Measure(s):

**Subjects.** After obtaining their written informed consent, 108 patients with CKD stage 3B-4 (defined as estimated GFR (eGFR) 15-44 ml/min/1.73m^2) and a serum bicarbonate level of 22-27 mEq/L, on 2 separate measurements (at least 1 day apart), will serve as subjects. **Relevant biological variables:** Men and women 21 years and older of all races/ethnicities will be included. Major inclusion/exclusion criteria are presented in the table below (Table 2). We chose a bicarbonate level of 22-27 mEq/L as this is a normal serum bicarbonate level and it is not standard of care to give alkali therapy when the bicarbonate level is >22 mEq/L. Hence, we can safely administer a placebo to these patients. Only stage 3B and not 3A are included as patients with stage 3B have an increased risk of adverse outcomes including cardiovascular outcomes and death compared to 3A. Patients will undergo screening for eGFR and serum bicarbonate at the Kidney Disease Research Center (KDRC) at the University of Colorado Anschutz Medical Campus. Estimated GFR will be calculated using the 4-variable Modified Diet Renal Disease prediction equation. Patients will be recruited from nephrology clinics at the University of Colorado where the PI has access to over 2,000 CKD patients. Additionally, patients will be recruited from our CKD database, which contains over 300 CKD patients willing to participate in clinical trials. The Health Data Compass services will also be used to generate a list of potential participants. Feasibility of recruitment is demonstrated by prior recruitment experience of the PI in the Vitamin D and Arterial Function in CKD Trial (see section 1a).

**Table 2**

Inclusion Criteria	Exclusion Criteria
--------------------	--------------------

**Figure 2. Percent FMDBA at baseline and 6-weeks after sodium bicarbonate administration**

 
• Age <math>\geq 21</math> years
 
• Serum bicarbonate 22-27 mEq/L on 2 separate measurements (at least 1 day apart)
 
• CKD stage 3B or 4 at time of screening (eGFR 15-44 ml/min/1.73m^2)
 
• Blood pressure <math><140/90</math> mm Hg prior to randomization
 
• BMI <math>< 40</math> kg/m^2 (FMD measurements can be inaccurate in severely obese patients).
 
• Able to provide consent
 
• Stable anti-hypertensive regimen for at least one month prior to randomization
 
• Not taking medications that interact with agents administered during experimental sessions (e.g. sildenafil interacts with nitroglycerin).
 
	
 
• Significant comorbid conditions that lead the investigator to conclude that life expectancy is less than 1 year
 
• Use of chronic daily oral alkali within the last 3 months (including sodium bicarbonate, calcium carbonate or baking soda)
 
• Uncontrolled hypertension
 
• Serum potassium <math>< 3.3</math> or <math>\geq 5.5</math> mEq/L at screening
 
• New York Heart Association Class 3 or 4 heart failure symptoms, known EF <math>\leq 30\%</math>, or hospital admission for heart failure within the past 3 months
 
• Factors judged to limit adherence to interventions
 
• Anticipated initiation of dialysis or kidney transplantation within 12 months
 
• Current participation in another research study
 
• Pregnancy or planning to become pregnant or currently breastfeeding
 
• Chronic use of supplemental oxygen
 
• Started on immunosuppression in the past 3 months
 
• Metal implant or implanted electrical device (patient will be unable to get MRI)
 

---	--

**Rigorous Experimental Design.** A 12-month **randomized, placebo-controlled, double-blinded study** with sodium bicarbonate will be conducted. The study will include 5 phases: screening, run-in, baseline, randomization and follow-up.

- **Screening:** Subjects will undergo screening for inclusion/exclusion criteria during a 1-2 week period.
- **Run-in:** A 1-month run-in period will occur if patients do not meet the BP goal of  $<140/90$  mmHg. The rationale for this run-in phase is to achieve a stable antihypertensive regimen and BP  $<140/90$  mmHg, such that changes in antihypertensive agents throughout the course of the study are minimal. This will allow for better isolation of the effect of bicarbonate on FMDBA, aPWV and LVMI. During the run-in phase, an up-titration of patients current angiotensin converting enzyme inhibitor or angiotensin receptor blocker to their maximum approved dose or other antihypertensive medication(s) will occur to reach a target BP of  $<140/90$  mmHg by their primary nephrologist or PCP. The duration of the run-in phase will be 4 weeks with weekly visits to achieve the target BP. The PI will contact the primary nephrologist/PCP of the patient if the BP is not at goal and discuss the need for medication changes. A BP  $<140/90$  mmHg is the standard of care for patients with CKD, hence we do not anticipate an issue with the primary nephrologist or PCP making changes to the BP regimen. If the patient is not able to achieve a BP of  $<140/90$  mmHg during this period, the participant will not be included in the study. This overall approach will allow for inclusion of the typical population of patients with CKD 3-4 and increase the generalizability of our expected results.
- **Baseline:** During the baseline phase FMDBA, aPWV, LVMI, serum basic chemistry panel, plasma AII, aldosterone, ET-1, serum T50, venous blood gas, and 24-hour urine collection measurements will be performed in all participants that are able to control their BP as described above.
- **Randomization:** Participants will be randomized with a 1:1 allocation ratio to treatment and placebo group using block randomization. List of randomization will be generated by the study statistician and sent to the study pharmacist (Belmar Pharmacy, Denver, CO) blinded to the PI. Study investigators, healthcare providers, participants, data collectors, outcome adjudicators and data analysts will be blinded to treatment assignment.
- **Follow-up:** The follow-up schedule includes:
  - 1 month: 1) remote or in-person safety visit (basic chemistry panel, adverse event assessment, gastrointestinal (GI) symptoms questionnaire, BP, pill compliance); 2) optional outcome measures: FMDBA, plasma AII, aldosterone, ET-1, and serum T50. Of note, aPWV will not be measured at 1 month as it is unlikely to change after only 4 weeks of treatment.
  - 3, 6 and 9 months: safety visit (basic chemistry panel, adverse event assessment, GI symptoms questionnaire, BP, pill compliance).
  - 6 months: in addition to the safety visit, outcome measures: FMDBA, aPWV, plasma AII, aldosterone, ET-1 and serum T50 and 24-hour urine collection.

- 12 months: 1) Adverse event assessment, GI symptoms questionnaire, BP, pill compliance; 2) outcome measures: FMDBA, aPWV, LVMI, serum basic chemistry panel, plasma AlI, aldosterone, ET-1, serum T50, venous blood gas, and 24-hour urine collection.

**4. Study Drug Dosing.** The study drugs (bicarbonate and the matched placebo) will be prepared by Belmar Pharmacy and will be identical in size, color, shape and taste. Each sodium bicarbonate capsule contains 7.7 mEq of bicarbonate and 178 mg of sodium. The matching placebo capsule will contain cornstarch. Belmar Pharmacy will bottle the capsules and label the bottles with code numbers to maintain the study's double blind and ship the bottles directly to the investigative site.

**a) Sodium bicarbonate:** Subjects randomly assigned to sodium bicarbonate therapy will receive 0.5 mEq/kg-lean body weight (LBW)/day for the entire 12 months. Participants will take ½ the daily dose in the morning and the other ½ in the evening. The number of capsules will be rounded to the nearest whole capsule. To reduce pill burden and increase compliance the maximum number of pills per day will be six.

**Rationale for sodium bicarbonate dose:** A dose of 0.5 mEq/kg-LBW/day has been shown to be safe and effective for treatment of metabolic acidosis in patients with CKD. Previous studies using this dose of sodium bicarbonate have not reported significant changes in edema, body weight or BP. In our **preliminary data**, sodium bicarbonate administration was not associated with an increase in BP or fluid gain in patients with CKD stage 3-4. Additionally, we will dose sodium bicarbonate based on LBW, not actual body weight. The volume of distribution of bicarbonate is approximately that of total body water. Total body water is dependent on lean body mass. We will use the following equations to determine LBW:

$$\text{LBW (kg)}_{\text{male}} = \frac{9270 \times \text{Wt}}{6680 + (216 \times \text{BMI})}$$

$$\text{LBW (kg)}_{\text{female}} = \frac{9270 \times \text{Wt}}{8780 + (244 \times \text{BMI})}$$

**b) Placebo:** Subjects randomly assigned to placebo will take the same number of capsules as if they were assigned to receive 0.5 mEq/kg-LBW/day of sodium bicarbonate. Participants will take ½ the daily dose in the morning and the other ½ in the evening. The number of capsules will be rounded to the nearest whole capsule. To reduce pill burden and increase compliance the maximum number of pills per day will be six.

**Rationale for placebo:** A placebo group is necessary to successfully complete our aims. If a placebo group were not included both the investigators and participants would know that they are receiving sodium bicarbonate, which could influence medical management and perception of side effects in the study. It is not standard of care to give sodium bicarbonate therapy when the serum bicarbonate is >22 mEq/L in CKD. Although unlikely in this 12-month study, serum bicarbonate may fall due to natural progression of CKD, particularly in the placebo group. As discussed in the safety section (see section 7), rescue therapy with open-label sodium bicarbonate will be initiated if the serum bicarbonate falls below 20 mEq/L on two consecutive measurements.

**5. Rationale for study duration.** The exact duration necessary for improving vascular function and LVMI in patients with CKD is unclear. From the study teams experience with other interventional studies evaluating vascular function, changes in FMDBA can be seen within 4-6 weeks (see preliminary data) and changes in aPWV can be seen after 6 months. We are proposing multiple follow-up measures of FMDBA (1 month (optional), 6 months and 12 months) and aPWV (6 months and 12 months) to determine short-term or long-term effects of bicarbonate. Changes in LVMI require longer periods of treatment and most published data use an intervention period of 6 months to 1 year. Accordingly, we propose to measure LVMI at 12 months.

Study	Population	Measure	Study Duration
Hayoz (2012) 	Postmenopausal women (n=125)	aPWV	38 weeks
Frimodt-Moller (2012) 	CKD stage 3-4 (n=67)	aPWV	6 months
Kao (2011) 	CKD stage 3 (n=67)	LVMI and FMD BA	9 months
Alkaishi (2013) 	CKD stage 4 (n=206)	LVMI	48 weeks
Ayus (2005) 	CKD stage 4 (n=101)	LVMI	6 months

## 7. Safety monitoring

**• Expected adverse events:** Sodium bicarbonate therapy may cause bloating, flatulence and abdominal discomfort. Although previous studies using similar doses of sodium bicarbonate have not reported significant changes in edema, body weight or BP, sodium bicarbonate may cause edema to develop or worsen thereby increasing BP. Previous studies suggest fluid retention is greater when sodium is accompanied by the chloride anion rather than the bicarbonate anion. As shown in our **preliminary data**, sodium bicarbonate did

not result in increased BP. Sodium bicarbonate also has the potential for causing metabolic alkalosis and hypokalemia if it is retained rather than excreted in the urine. These expected adverse events will be monitored during the course of the study and in general, can be medically managed by adjusting antihypertensive and/or diuretic agents, providing potassium replacement and by dietary changes. Of note, none of these adverse events were observed in our short-term pilot study.

- **Dose reduction and discontinuation:**

- Serum bicarbonate >28 mEq/L: The intervention dose (study drug) will be reduced by 50% by the PI and diuretics will be adjusted as appropriate by the primary nephrologist or PCP. The PI will contact the primary nephrologist or PCP by phone or email and discuss changes in diuretics. The participant will return for a visit one week later to have serum chemistries rechecked. If the bicarbonate remains >28 mEq/L the intervention will be stopped by the PI and the participant will have serum bicarbonate measured weekly until it is <28 mEq/L. Plasma ionized calcium will be checked if bicarbonate is >30 mEq/L at any visit since an increase in pH can decrease the ionized calcium concentration. Management of low ionized calcium will be at the discretion of the PI based on symptoms reported by the patient. The PI will contact the primary nephrologist or PCP if she believes calcium supplementation is necessary and the primary physician will order the medication.
- Systolic blood pressure ≥ 160 or diastolic blood pressure ≥ 80 mmHg: Potential reasons for uncontrolled BP, such as poor compliance or running out of medications will be evaluated and managed appropriately. If an identifiable cause is not found, the PI will contact the primary nephrologist or PCP to increase anti-hypertensive medications and/or diuretics. The participant will return 1 week later for follow-up. If BP remains >160/80 mmHg at the second visit, the PI will again contact the primary nephrologist or PCP for medication changes and the intervention dose (study drug) will be reduced by 50% by the PI. The participant will return 1 week later. If BP remains unchanged at the third visit, the intervention will be stopped by the PI and the PI will contact the primary physician for escalation of medications. Participants will continue to have PRN visits weekly until BP is <160/80 mmHg.
- Serum potassium < 3.0 mEq/L: The intervention dose will be reduced by 50% by the PI and the PI will contact the primary nephrologist or PCP to discuss adjusting diuretics as appropriate and prescribing potassium replacement. The participant will return 1 week later for repeat labs. If serum potassium remains < 3.0 mEq/L, the intervention will be discontinued by the PI. The participant will return weekly until serum potassium is > 3.0 mEq/L.
- Severe edema: If in the opinion of the PI severe edema (4+) is present and another etiology cannot be identified the dose of the intervention will be reduced by 50% and the PI will contact the primary nephrologist or PCP to make adjustments to diuretics. If fluid retention remains severe at follow-up visits, the intervention (study drug) will be discontinued.
- Rescue therapy with oral sodium bicarbonate: Rescue therapy with open-label sodium bicarbonate will be initiated by the PI if serum bicarbonate is <20 mEq/L on 2 consecutive measurements at least 1 week apart since a level <20 mEq/L is associated with adverse outcomes. In this instance, open-labeled sodium bicarbonate will be given to target serum bicarbonate of 20-22 mEq/L. Participants will not discontinue study medications if open-labeled sodium bicarbonate is prescribed.

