  - Serum bicarbonate >26 mEq/L: The intervention dose will be reduced by 50% and diuretics will be adjusted as appropriate. The participant will return for a visit one week later to have serum chemistries rechecked. If the bicarbonate remains >26 mEq/L the intervention will be stopped and the participant will have serum bicarbonate measured weekly until it is <26 mEq/L. Plasma ionized calcium will be checked if bicarbonate is >26 mEq/L at any visit since an increase in pH can decrease the ionized calcium concentration. Management of low ionized calcium will be at the discretion of the PI based on symptoms reported by the patient.
  - Systolic blood pressure ≥ 160 or diastolic blood pressure ≥ 80 mmHg: Potential reasons for uncontrolled BP, such as poor compliance or running out of medications will be evaluated and managed appropriately. If an identifiable cause is not found, the PI will increase anti-hypertensive medications and/or diuretics. The participant will return 1 week later for follow-up. If BP remains >160/80 mmHg at the second visit, medications will again be increased and the intervention dose will be reduced by 50%. The participant will return 1 week later. If BP remains unchanged at the third visit, the intervention will be stopped and medications will again be escalated. Participants will continue to have PRN visits weekly until BP is <160/80 mmHg.
  - Serum potassium < 3.0 mEq/L: The intervention dose will be reduced by 50%, diuretics will be adjusted as appropriate and potassium replacement will be prescribed. The participant will return 1 week later for repeat labs. If serum potassium remains < 3.0 mEq/L, the intervention will be discontinued. The participant will return weekly until serum potassium is > 3.0 mEq/L.
  - Severe edema: If in the opinion of the PI severe edema (4+) is present and another etiology cannot be identified the dose of the intervention will be reduced by 50% and diuretics will be adjusted. If fluid retention remains severe at follow-up visits, the intervention will be discontinued.

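### The protocol gives two different serum bicarbonate limits for halving and stopping study drug (>28 and >26 mEq/L), and the lower one lies inside the 22-27 mEq/L eligibility range

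*Combined protocol and SAP*

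**What the plan says.** The dose-reduction rule for high bicarbonate appears twice in the protocol dated June 17, 2020.

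- Section IV.7, Safety monitoring: "Serum bicarbonate >28 mEq/L: The intervention dose (study drug) will be reduced by 50% by the PI". Drug is stopped if the value is still above 28 a week later, weekly checks end below 28, and "Plasma ionized calcium will be checked if bicarbonate is >30 mEq/L at any visit".
- Protection of Human Subjects, item 5, Data and Safety Monitoring Plan: "Serum bicarbonate >26 mEq/L: The intervention dose will be reduced by 50% and diuretics will be adjusted as appropriate". Then "If the bicarbonate remains >26 mEq/L the intervention will be stopped", "the participant will have serum bicarbonate measured weekly until it is <26 mEq/L" and "Plasma ionized calcium will be checked if bicarbonate is >26 mEq/L at any visit".

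Eligibility, in section IV.A (Subjects), requires "a serum bicarbonate level of 22-27 mEq/L, on 2 separate measurements (at least 1 day apart), will serve as subjects". Table 2 gives the same range.

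**The concern.** Both texts are operative instructions with the same sequence: halve, recheck at one week, stop, check weekly. No statement elsewhere says which applies. For any value above 26 and up to 28, one text keeps the participant on full dose while the other halves the dose and may stop it. Whichever the investigator follows, the other section is breached. The DSMB is charged with assuring protocol compliance under the plan that contains the 26 limit, so it could be checking conduct against a different number from the one in the methods.

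The >26 limit has a second problem. It is 1 mEq/L below the top of the eligibility range, so a participant can qualify at a level that already meets the criterion for halving.

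**Working it through.** **1. The two rules side by side (mEq/L)**

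| Action | Section IV.7 | Data and Safety Monitoring Plan | Gap |
|---|---|---|---|
| Halve the dose | >28 | >26 | 2 |
| Stop if still high at one week | >28 | >26 | 2 |
| End weekly checks | <28 | <26 | 2 |
| Check ionized calcium | >30 | >26 | 4 |

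All four numbers differ. This table establishes the contradiction, and no calculation is needed for it.

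**2. Position against eligibility**

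Eligibility runs from 22 to 27. Since 22 < 26 < 27, the >26 limit is inside the range. The >28 limit is 1 mEq/L above its top.

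**3. Illustration: how many could enter above 26**

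The plan states no figure to reproduce. Inputs are the mean of 22.9 and SD of 2.9 mEq/L reported for the site's 128 CKD 3B-4 patients (Preliminary Studies, item d). The assumption is that bicarbonate is normal with these values, restricted to the eligible range on a single measurement.

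- Continuous values: P(>26 given 22-27) = [Φ(1.414) − Φ(1.069)] / [Φ(1.414) − Φ(−0.310)] = (0.9213 − 0.8575) / (0.9213 − 0.3781) = 0.118.
- Whole-number reporting, so only a value of 27 exceeds 26: [Φ(1.586) − Φ(1.241)] / [Φ(1.586) − Φ(−0.483)] = (0.9437 − 0.8928) / (0.9437 − 0.3146) = 0.081.

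The result is about 8-12%. If the mean is varied over 22-24.5 and the SD over 2-3.5, the range is 3-18% for continuous values and 2-14% for whole numbers.

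**4. Allowing for two screening values and a recheck**

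This was simulated with 4,000,000 draws, total SD 2.9, both screening values in 22-27, continuous values, and no drug or diuretic effect. The within-person SD is assumed, because the protocol gives none.

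| Within-person SD | Next test >26 | Next test and recheck >26 | Next test >28 | Both >28 |
|---|---|---|---|---|
| 0.5 | 10.6% | 6.6% | 0.1% | <0.1% |
| 1.0 | 13.0% | 5.7% | 0.8% | 0.1% |
| 1.5 | 16.5% | 6.1% | 2.4% | 0.4% |

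**5. What these figures do not measure**

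Steps 3 and 4 describe only the overlap with eligibility, at one visit and without drug. They are not the burden of either rule over the trial. If the same simulation adds an assumed uniform rise of 2 mEq/L on active drug, about 51-53% exceed 26 and 11-16% exceed 28 at one visit. The rise in the eligible population is not known. The pilot's rise of 22.4 − 19.6 = 2.8 mEq/L came from patients selected for bicarbonate of 16-22.

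**The case against.** The strongest reply is that the 26 limit is a leftover and that everyone would use 28. Much of this stands. Section IV.7 is the fuller text: it names who acts and how the treating physician is contacted. It is also the section to which the placebo rationale sends the reader for the rescue rule. Only >28 is compatible with eligibility up to 27. Blood-pressure targets show a similar mismatch (<130/80 in the Table of Detailed Visits and section 12, against <140/90 in Table 2 and the run-in), which suggests incomplete harmonisation, although that is inference. None of this tells the investigator or the DSMB which number governs.

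A reader might infer the opposite, that >26 was meant or that the evidence is evenly balanced, because Background item 9 links persistent bicarbonate above 26 to heart failure events and death. The documents do not support that reading. The Background also reports adverse signals above 24 and at 25 or more (items 8b and 9) and higher mortality above 29 (item 8c), and it puts the lowest risk of CKD progression near 28 (item 8a). Several of these signals start below both limits, so they do not single out 26.

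A reader might also infer bias between arms or lost power. The rule applies to both arms, the investigators are blinded, and the primary analysis is intention-to-treat. The power calculations in section 10 make no assumption about delivered dose, and the documents give no means of turning halved doses into a smaller effect on FMD or aPWV.

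**Conclusion.** The contradiction is certain and rests on the text alone. Two incompatible limits for halving and stopping study drug, and for the related checks, stand in the current protocol. They differ by 2 mEq/L for dosing and 4 mEq/L for ionized calcium. The safety rule has to be corrected whatever the true distribution of bicarbonate.

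The overlap with eligibility is also certain in kind. Its size, about 8-12% entering above 26, depends on the normal distribution and the site's earlier cohort applying to this trial, and is illustration only.

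The internal evidence favours >28 without stating it. The point concerns clarity and safety of conduct. It is not a finding about validity of the treatment comparison.

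**What to change.** Amend the Data and Safety Monitoring Plan to match section IV.7: above 28 to halve, still above 28 at one week to stop, below 28 to end weekly checks, and above 30 for ionized calcium. Because this is a clinical safety limit, the investigators, IRB and DSMB should confirm it against the adverse signals at higher bicarbonate in Background items 8 and 9, and record that they did so.

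The cost is one protocol amendment, with no extra patients or procedures. Lowering the eligibility ceiling is not part of the fix. With the limit at 28 the overlap with the eligibility range disappears. A ceiling of 26 would, on the simulation above, exclude about 14-21% of otherwise eligible patients and still leave 3-12% of those admitted above 26 at the next test.

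### The on-study blood pressure rule starts at a diastolic of 80 mmHg, inside the <140/90 entry range, and the protocol gives two different run-in goals

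*Combined protocol and SAP*

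**What the plan says.** **Entry and run-in.** Table 2 requires blood pressure below 140/90 "mm Hg prior to randomization" and also "Stable anti-hypertensive regimen for at least one month prior to randomization". The Run-in paragraph uses 140/90 three times over. It is the goal that decides who needs a run-in and the target of titration. It is described as care that patients should already be receiving (below 140/90 "mmHg is the standard of care for patients with CKD"). It is also the exclusion rule: for a patient who cannot get below 140/90 "mmHg during this period, the participant will not be included in the study". The stated purpose is a stable regimen, "such that changes in antihypertensive agents throughout the course of the study are minimal", so that the effect of bicarbonate on FMD, aPWV and LVMI can be isolated.

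**On study.** Section 7, under dose reduction and discontinuation, opens the rule with "Systolic blood pressure ≥ 160 or diastolic blood pressure ≥ 80 mmHg: Potential reasons for uncontrolled BP". If no cause is found, the PI asks the primary nephrologist or PCP to increase antihypertensives and/or diuretics, and the participant returns in a week. The next step reads: "If BP remains >160/80 mmHg at the second visit, the PI will again contact the primary nephrologist or PCP for medication changes", and study drug is halved. If pressure is unchanged at a third visit, study drug is stopped. Weekly visits continue until pressure is below 160/80. The Data and Safety Monitoring Plan repeats the same thresholds, but there the PI makes the medication increase directly.

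**A second run-in goal.** The Table of Detailed Visits and section 12 (Potential Problems and Alternative Strategies) both put the run-in goal at <130/80.

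**The concern.** The first step of the safety rule needs only one component, and its diastolic limit lies within the range that the entry criterion accepts. A participant enrolled correctly at 134/85, and still at 134/85 at a follow-up visit, counts as having uncontrolled pressure although nothing has changed since randomization. Followed literally, the rule brings about the medication changes that the run-in was designed to avoid. Those changes bear on FMD, aPWV and LVMI, for which the protocol itself names systolic pressure as an important determinant. Participants with stage 3B-4 CKD would also carry extra visits and drug escalation that the entry rule implies they do not need.

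Two further points follow. The later limit, written >160/80, does not say whether one component is enough; if it is, the rule can also halve and then stop study drug in these participants. And with two run-in goals 10 mmHg apart on each component, staff cannot tell from the protocol who needs the run-in.

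**Working it through.** The core of the check is a comparison of thresholds, all taken from the protocol.

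| Rule | Where | Systolic | Diastolic |
|---|---|---|---|
| Entry limit | Table 2 | <140 | <90 |
| Run-in goal and exclusion | Run-in paragraph | <140 | <90 |
| Run-in goal | Table of Detailed Visits; section 12 | <130 | <80 |
| On-study trigger (either component) | Section 7; Data and Safety Monitoring Plan | ≥160 | ≥80 |
| Second-visit limit (either or both not stated) | Same two sections | >160 | >80 |

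**Margins.** Trigger minus entry limit is 160 − 140 = +20 mmHg systolic and 80 − 90 = −10 mmHg diastolic.

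**First step.** Taking whole-number readings, the highest eligible systolic is 139, below 160, so an eligible participant can meet the trigger only through the diastolic limb. Every eligible diastolic from 80 to 89 meets it. Under a <130/80 entry goal the highest diastolic is 79 and none does. With entry at <140/90 and a diastolic trigger of 90, none does either.

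**Later steps.** If either component suffices, an unchanged diastolic of 81-89 meets >80 and leads to halving and then stopping. A diastolic of exactly 80 meets the first step but not the second. If both components are needed, systolic would have to exceed 160, so no one still inside the entry range gets past the first step.

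**What loss of drug could mean for power (illustration only).** The protocol gives no distribution of diastolic pressure, so the following rests on assumptions: the either-component reading, and diastolic pressure at entry normal with SD 10, truncated below 90, with mean 65, 70, 75 or 80 before truncation.

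- Share starting at 80-89: f = P(80 ≤ DBP < 90 | DBP < 90).
- A fraction g of these lose the whole treatment effect, so p = g × f of the active arm loses it.
- Expected difference: 1.0 × (1 − p).
- Active-arm variance: 1.5² + p(1 − p) × 1.0². The SD used is the square root of the average of this and 1.5².
- Test: two-sample t, two-sided 0.025, 54 per group, noncentral t.

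The plan's own aPWV figure comes first: difference 1.0 m/s, SD 1.5 and p = 0 give 88.1%, agreeing with the stated 88%.

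| Assumed mean DBP | f | Power, g = 0.25 | Power, g = 1 |
|---|---|---|---|
| 65 | 6.1% | 86.9% | 83.0% |
| 70 | 13.9% | 85.3% | 74.8% |
| 75 | 25.9% | 82.6% | 59.6% |
| 80 | 40.6% | 78.9% | 39.8% |

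A worked cell, for mean 80 and g = 1: p = 0.406; difference 0.594; active variance 2.25 + 0.406 × 0.594 = 2.491; SD = √((2.25 + 2.491)/2) = 1.540; power 39.8%. Simulation with 40,000 runs per cell agreed within 0.004.

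If the affected participants instead kept half the effect, the g = 1 column would read 85.8%, 82.5%, 76.5% and 68.1%. On the plan's FMD inputs (1.5%, SD 0.8%), the worst cell, p = 0.406, still gives 99.5%.

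These figures are not bounds. They leave out participants whose diastolic rises to 80 or more on study, and g = 1 supposes that the medication increases never work.

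**The case against.** The certain consequence is modest. In section 7 the first step is a search for a cause, and only then a request to the treating physician, who makes any change. Table 2 asks for a stable regimen before randomization only, and the run-in aims for minimal on-study changes, not none. Section 7 also foresees managing adverse events by adjusting antihypertensives and diuretics. Loss of study drug needs the either-component reading and two failed medication increases. The power figures rest on assumed inputs and run from negligible to large according to the choice. Blinded randomization, ITT analysis and the planned adjustment for blood pressure limit bias between arms.

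A cautious diastolic limit could also be deliberate, since section 7 warns that "sodium bicarbonate may cause edema to develop or worsen thereby increasing BP". And the overlap exists only if <140/90 governs, so the root defect may simply be an inconsistent goal.

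Most of this stands as a limit on the size of the problem. Drug loss and loss of power are possible, not shown. But none of it removes the overlap. No text says that the diastolic trigger is meant to lie below the entry limit. The safety sections describe as uncontrolled a pressure that Table 2 accepts. Foreseeing changes for adverse events does not explain requiring them in participants who have not changed. <140/90 is the better reading of the entry rule, because it is the formal inclusion criterion.

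**Conclusion.** The concern holds. Under the formal entry criterion, the whole diastolic band 80-89 is both eligible and at the first step of the safety rule, and the two run-in goals contradict each other. This much needs no assumption beyond an unchanged reading with no identifiable cause. How many participants are affected cannot be derived from the protocol.

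Any loss of study drug depends on how the >160/80 limit is read. It is zero by this route for anyone with systolic at or below 160 if both components are required. Under the other reading, a noticeable loss of aPWV power is possible, but its size depends on the assumed diastolic distribution and on how many participants progress; FMD power is not at risk on the plan's inputs. The point should be fixed because an operative safety rule misfires when followed exactly and the correction is cheap. It does not make the trial invalid.

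**What to change.** Use one blood pressure goal in Table 2, the Run-in paragraph, the Table of Detailed Visits and section 12. Set the diastolic trigger and the later diastolic limits in section 7 and the Data and Safety Monitoring Plan so that no one meeting that goal already meets them. One workable version keeps <140/90, corrects the two <130/80 entries, and raises the diastolic limits to at least 90. State the second-visit and closing limits by component, saying whether systolic or diastolic alone is enough, in identical words in both sections. The same edit can settle who makes the medication change, since the two sections differ.

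Raising a safety limit for a sodium-containing drug that may raise blood pressure means intervening later, so the investigators and the DSMB should confirm the values. They should also say how participants already managed under the present limit are handled.

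The cost is one protocol amendment, with no extra visits or staff if <140/90 is kept. Choosing <130/80 at entry also removes the overlap, but sends more patients through the run-in.
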